## 5. STUDY POPULATION

### 5.1. Subject Inclusion Criteria

Unless otherwise noted, subjects must satisfy each inclusion criterion to participate in the study. Inclusion criteria will be assessed at the Screening Visit, prior to renal biopsy, and before each REACT injection unless otherwise specified.

1. The subject is male or female, 30 to 65 years of age on the date of informed consent.
2. The subject has an established diagnosis of T2DM.
3. The subject has an established diagnosis of diabetic nephropathy as the underlying cause of renal disease.
4. The subject has an established diagnosis of CKD not requiring renal dialysis, defined as having an eGFR between 14 and 20 mL/min/1.73m^2 inclusive at the Screening Visit and prior to REACT injection.
5. The subject has blood pressure less than 150/90 at the Screening Visit, prior to renal biopsy, and prior to REACT injection(s). At the time of the biopsy and injections, the subject's BP should not be significantly below the previously recorded stable pressure.
6. The subject has stable blood pressure and is maintained on a stable anti-hypertensive medication regimen, if treatment for hypertension is necessary. If treatment includes an angiotensin-converting-enzyme inhibitor (ACEI) or an angiotensin receptor blocker (ARB), that treatment must have been initiated at least 8 weeks prior to renal biopsy. Treatment must be stable during the 6-week period immediately prior to REACT injection. Stable treatment is defined as dose adjustment to no less than one half of the current dosage or to no more than 2 times the current dosage. Dose interruptions up to 7 days due to medical necessity are allowed.
7. A minimum of 3 measurements of eGFR or sCr should be obtained at least 3 months apart prior to the Screening Visit or within the previous 24 months to define the rate of progression of CKD. The subject should have adequate, historical clinical data to provide a reasonable estimate of the rate of progression of CKD. The Medical Monitor may be consulted to ensure there is sufficient data.
8. The subject is willing and able to refrain from NSAID consumption (including aspirin) as well as clopidogrel, prasugrel, or other platelet inhibitors during the period beginning 7 days before through 7 days after both the renal biopsy and REACT injection(s).

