## 5.2. Subject Exclusion Criteria

Subjects who satisfy any exclusion criterion listed below are not eligible to participate in the study. Exclusion criteria will be assessed at the Screening Visit, before renal biopsy, and before each REACT injection unless otherwise noted.

1. The subject has a history of type 1 diabetes mellitus.
2. The subject has a history of renal transplantation.
3. The subject has a serum HbA1c level greater than 10% at the Screening Visit.
4. The subject has uncontrolled diabetes (defined as metabolically unstable by the Investigator).
5. The subject has hemoglobin levels less than 9 g/dL prior to each REACT injection.
6. The subject has abnormal coagulation status as measured by activated partial thromboplastin time (APTT), prothrombin time international normalized ratio (PT INR), and/or platelet count at the Screening Visit.
7. The subject has a bleeding disorder(s) or is taking anticoagulants, such as Coumadin® (warfarin) or direct thrombin inhibitors that, in the judgment of the Investigator, would interfere with the performance of study procedures.
8. The subject has small kidneys (average size less than 9 cm) or has only one kidney, as assessed by ultrasound and/or MRI prior to renal biopsy, unless earlier radiology reports (generated within 1 year of the Screening Visit) are made available to confirm kidney size and number.
9. The subject has a known allergy or contraindication(s), or has experienced severe systemic reaction(s) to kanamycin or structurally similar aminoglycoside antibiotic(s)
10. The subject has a history of anaphylactic or severe systemic reaction(s) or contraindication(s) to human blood products or materials of animal origin (e.g., bovine, porcine).
11. The subject is not a good candidate to undergo percutaneous REACT injection, in the judgment of the surgeon or physician who will perform the procedure. This includes individuals who are morbidly obese (defined as BMI greater than 45 kg/m^2), have excessive fat surrounding the kidney, or who are otherwise at excessive risk for serious complications.
12. The subject has a history of severe systemic reaction(s) or any contraindication to local anesthetics or sedatives.
13. The subject has a clinically significant infection requiring parenteral antibiotics within 6 weeks of REACT injection.
14. The subject has acute kidney injury or has experienced a rapid decline in renal function during the last 3 months prior to REACT injection.

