### 6.3. REACT Injection

Due to shipping and manufacturing schedules, REACT injection should be scheduled on a Wednesday, Thursday, or Friday. If it is necessary to schedule the REACT injection on a Tuesday, the site should contact ProKidney in advance to make certain that a Tuesday delivery can be accommodated. The REACT injection should not be scheduled on a Monday.

Subjects will report to the clinic 10 to 14 days before the scheduled REACT injection for pre-treatment assessments. If the subject remains eligible, based on verification of inclusion and exclusion criteria, the site will perform a renal scintigraphy study and contact ProKidney indicating that the REACT product should be produced for that particular subject.

It is anticipated that all subjects will receive two planned REACT injections to allow dose-finding and to evaluate the duration of effects. As indicated on the time and events tables (i.e., [Table 1](#)), the series of 2 REACT injections will be administered 6 months apart with a study visit window of 4 weeks. Regardless, **every attempt should be made to ensure that the second REACT injection is administered 6 months after the first injection**. In the event that the subject cannot schedule his/her second REACT injection 6 months after receiving the first injection or cannot keep his/her scheduled 6-month visit, ProKidney and the Medical Monitor must be notified immediately. The expectation is that the subject and the clinical center will accommodate the Sponsor's preference that the series of 2 REACT injections should be administered no more than 6 months apart.

In some cases, a subject or the Investigator may decide to postpone or withhold the second REACT injection. For example, if there appears to be any untoward safety risk, or rapid deterioration of renal function, or the development of uncontrolled diabetes or uncontrolled hypertension, or the development a malignancy or an intercurrent infection, then the second REACT injection should not be administered.

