4.9 Analysis Periods

The following analysis periods will be defined as:

- Pre-Injection Period: from the start day of biopsy to the first REACT injection.
- Acute First Injection Period: from the first REACT injection to 1 month following the first REACT injection. The acute first injection period is a subset of the inter-injection period defined below.
- Inter-Injection Period: from the first REACT injection to either the second REACT injection or (if no such second injection was delivered) trial withdrawal or completion.
- Acute Second Injection Period: from the second REACT injection to 1 month following the second REACT injection. The acute second injection period is a subset of the post-second-injection period defined below.
- Post-Second Injection Period: from the second REACT injection to trial withdrawal or completion. This period will not apply to participants for whom only one REACT injection was delivered.
- Post-Injection Period: from the first REACT injection to trial withdrawal or completion. This period includes both the inter-injection and post-second injection periods.

[figure not shown]
If necessary, imputed dates will be used to determine the analysis period for adverse events.

Figure 1. Analysis Period Diagram for Subjects that Received Two Injections

Abbreviations: EOS = End of Study

Figure 2. Analysis Period Diagram for Subjects that Received One Injection

Abbreviations: EOS = End of Study

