6.3.4 Rate of Progression of Renal Disease

Using the IAS, the rate of progression of renal disease will be assessed graphically for eGFR as estimated by the 2009 CKD-EPI serum creatinine equation, serum creatinine, and 24 hour urine albumin, and 24 hour urine protein. For each subject a plot of the lab result versus time (in study days) will be displayed, showing vertical lines at biopsy date, 1st and 2nd injection, and the initiation of dialysis, if it is administered. Additionally, for eGFR, the rate of progression of renal disease will be assessed by estimating the annualized eGFR slope over time for each subject. Each subject will serve as his or her own control. The subject's previous medical history, which must include a minimum of 6 months of observation of renal function, will serve as the control for rate of progression of renal insufficiency. The historical eGFR measurements as well as all on study measurements taken prior to the first REACT injection will constitute the pre-injection period for this analysis.

The annualized rate of eGFR decline for the pre-injection, post-second injection, and post-injection periods will be estimated separately by linear mixed effects models. That is, separate models will be fit for each of the specific time periods: pre-injection, post-second injection, and post-injection periods. Each subject with a minimum of 3 observations during the period of interest will be modeled. The model will include unscheduled visits, and only the last measurement if there was a re-test on the same day.

For the pre-injection period, the linear mixed effects model will include eGFR as the dependent variable, and time (in years, derived as study day/365) as the independent variable. To account for between-subject variability in eGFR trajectories, random slopes and intercepts will be included. An unstructured covariance matrix will be used for the model. If the model cannot be fit with the unstructured covariance matrix, the following structure will be tried in the order listed below (decreasing number of parameters) until the one of them fit the model:

1. First-order autoregressive moving average (ARMA(1,1))
2. First-order autoregressive (AR(1))
3. Compound symmetry (CS)
4. Variance Components (VC)

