For the post-secondary period, and separately for the post-injection period as a whole, linear mixed effects models will be fit including eGFR as the dependent variable, time (in years, derived as study day/365) as the independent variable, and baseline eGFR as a covariate. To account for between-subject variability in eGFR trajectories, random slopes and intercepts will be included. An unstructured covariance matrix will be used for the model. If the model cannot be fit with the unstructured covariance matrix, the same procedure as for the pre-injection period will be followed.

A table will be presented to display the following for each time period of interest: number of subjects included in the model, the estimated slope for the time variable, and the associated standard error. If no model can be fit, the table will simply display a message "Model did not converge."

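### The post-second-injection eGFR slope lacks a like-for-like pre-injection comparator, because fast decliners are kept from injection 2

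*SAP*

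**What the plan says.** SAP 6.3.4 works in the injection analysis set, which SAP 4.2 defines as subjects with at least one injection. It states the own-control principle, and then "separate models will be fit for each of the specific time periods: pre-injection, post-second injection, and post-injection periods". The only entry condition is "Each subject with a minimum of 3 observations during the period of interest will be modeled". For the post-second-injection period, SAP 4.9 adds: "This period will not apply to participants for whom only one REACT injection was delivered". The output table gives, for each period, the "number of subjects included in the model, the estimated slope for the time variable, and the associated standard error". No common subject set and no within-subject slope difference is planned.

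Receipt of injection 2 depends on renal course. Protocol 6.3 says it should not be given "if there appears to be any untoward safety risk, or rapid deterioration of renal function", among other reasons. Exclusion 14 in Protocol 5.2, checked before each injection, bars a subject who "has experienced a rapid decline in renal function during the last 3 months prior to REACT injection". Whether the eGFR range of 14 to 20 also applies again is less clear. The lead-in to Protocol 5.1 says "Inclusion criteria will be assessed at the Screening Visit, prior to renal biopsy, and before each REACT injection unless otherwise specified", while criterion 4 sets the range "inclusive at the Screening Visit and prior to REACT injection", in the singular, and Protocol 6.1 ties it to the Screening Visit.

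**The concern.** The two rows a reader will naturally compare describe different people. At least three historical eGFR or creatinine values are an entry criterion (Protocol 5.1, criterion 7), so almost every injected subject enters the pre-injection model. The post-second-injection model loses everyone who did not get injection 2, and the withholding rules act on the quantity being estimated, the rate of decline. Removing fast decliners from the later row but not the earlier one makes the later slope flatter whether or not the product works.

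The post-injection models include baseline eGFR, defined in SAP 4.7 as the last value before the first injection. That adjusts for level, not for earlier slope, so it does not repair the mismatch.

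The row matters because Protocol section 2 proposes that the product will slow eGFR decline over the 24 months after the last injection. For a subject given two injections, that span is the post-second-injection period.

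**Working it through.** The plan states no figure to reproduce: the sample size is up to 10, with no precision calculation and no test. The question is how large the gap between the two rows is when treatment does nothing.

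**Where the gap comes from.** Let s be a subject's constant true slope and p the proportion who receive injection 2. With no treatment effect,

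gap = mean s (recipients) − mean s (all injected) = (1 − p) × [mean s (recipients) − mean s (non-recipients)].

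It is zero only if everyone receives injection 2 or if receipt is unrelated to slope. An example, with mean slope −5, slope SD 3, measurement SD 1, and injection 2 withheld after an observed six-month fall above 3: p = 0.60 and recipients average −3.56. Non-recipients then average (−5.00 + 0.60 × 3.56)/0.40 = −7.16, and the gap is 0.40 × (−3.56 + 7.16) = 1.44 per year.

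**Why the 14–20 window would bite.** The largest annual decline that keeps eGFR at 14 or above six months later is (baseline − 14)/0.5. That is 2 per year from a baseline of 15, 4 from 16 and 6 from 17.

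**Simulation, no treatment effect.** All rates and variances are assumptions. Mean slope is −2, −4 or −6 mL/min/1.73 m² per year, slope SD 2 or 3, and measurement SD 1 or 1.5, giving 12 scenarios of 400,000 draws each. Screening and pre-injection values, 0.2 years apart, must both be observed within 14–20; eGFR is measured again 0.5 years after injection 1. Pre-injection slopes use assumed times of −24, −18, −12 and −6 months plus the two qualifying values. Post-second-injection slopes use months 1, 2, 3, 6, 9, 12, 15, 18, 21 and 24. Least-squares slopes per subject are averaged as an approximation to the mixed model. The gap is the later slope minus the pre-injection slope, per year; positive means flatter.

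| Injection 2 withheld if | Without injection 2 | Gap, all-subject pre row | Gap, matched pre row |
|---|---|---|---|
| never (check) | none | −0.02 to 0.00 | – |
| eGFR outside 14–20, one measurement | 25–60% | 0.26–1.77 | 0.03–0.18 |
| eGFR outside 14–20, one repeat allowed | 15–50% | 0.19–1.57 | 0.02–0.16 |
| observed fall of at least 3 | 13–53% | 0.27–1.75 | 0.03–0.21 |
| observed fall of at least 4 | 4–37% | 0.11–1.13 | 0.01–0.15 |
| observed fall of at least 5 | 1–23% | 0.03–0.71 | 0.00–0.08 |

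The matched row is the pre-injection slope in injection 2 recipients only.

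**Other assumptions.** With baseline uniform on 14–20, mean slope −3 or −5, slope SD 2–4 and measurement SD 1–1.5, 53–81% receive injection 2. The recipients' true slope is 0.3–2.2 per year flatter than that of all injected subjects.

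**The SAP's own model at n = 10.** A random intercept and slope model was fitted to 200 simulated trials (mean slope −4, SD 3, residual SD 1.2, injection 2 only if eGFR is 14–20, values dropped once true eGFR falls below 7). On average 6.5 of 10 subjects received injection 2. Mean slopes were −3.85 (pre-injection, all), −3.00 (pre-injection, recipients) and −2.98 (post-second injection). The gap is −2.98 + 3.85 = 0.87 against the planned row and −2.98 + 3.00 = 0.02 against the matched row.

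**The case against.** The best case for leaving the plan alone has four parts.

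- **A near-matched comparison already exists.** The whole post-injection model covers almost the same subjects as the pre-injection model, and the SAP neither names the post-second-injection slope as the main contrast nor plans a slope difference.
- **The mismatch is visible.** The number of subjects is printed for each model, disposition shows who had one or two injections, and each subject has an eGFR plot marking both injections.
- **It may not arise.** The plan anticipates two injections for everyone, and some withholding reasons, such as infection or subject choice, need not relate to slope.
- **The size is assumed and often within noise.** The largest gaps need the unsettled 14–20 reading, and the fall thresholds are invented because rapid deterioration has no numeric definition. With measurement SD 1.5, the difference of two readings has a noise SD of √2 × 1.5 = 2.1, so at a threshold of 3 many withholdings would be noise. From 10 injected subjects at threshold 4, the gap is 0.17–1.18 standard errors, and below one in 10 of 12 scenarios.

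All of this stands as a limit on consequence. None of it corrects the contrast. Printed counts and plots show that subjects differ but do not supply the matched slope, and the sound post-injection row does not mend the other one. A gap below one standard error is still a systematic shift towards apparent benefit.

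**Conclusion.** The concern holds. As written, the post-second-injection slope is set beside a pre-injection slope from a wider group that includes subjects removed for declining fast, contrary to the SAP's own-control principle. Under the assumed decline rates and no treatment effect, the spurious flattening is about 0.1–1.1 mL/min/1.73 m² per year if only an observed fall of at least 4 withholds injection 2 (0.03–1.8 across thresholds 3 to 5). It is 0.2–1.8 if the 14–20 window also governs. The direction favoured the product in every scenario with selection. The finding does not depend on the window, since the rapid-deterioration rule alone produces the gap.

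For scale, the standard error of the mean true slope among those retained from 10 subjects under the window rule is about 0.6–1.2, so at mean declines of 2–4 per year the gap is around or below one standard error. The damage is confined to one of two exploratory, descriptive post-treatment slopes.

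**What to change.** In SAP 6.3.4, add one row to the slope table: the pre-injection model refitted only in the subjects who enter the post-second-injection model, with at least three observations in both periods. State that the own-control comparison for the post-second-injection period uses this row. Keep the all-subject pre-injection slope as the comparator for the whole post-injection slope.

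This needs no new data or visits. The matched row has fewer subjects and a larger standard error, and the model may fail to converge when many subjects miss injection 2; the SAP already provides a message for that case. A small bias remains, up to about 0.2 per year in the simulation, because entry and withholding decisions rest on noisy eGFR values. The row also cannot correct for selection on decline that first appears after injection 1, and a table footnote should say so. If every subject receives injection 2 and contributes enough data, the row simply repeats the existing one.

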## 9.4. Efficacy Analysis

The primary efficacy endpoint is serial measurements of eGFR obtained at 1, 3, 6, 12, 15, 18, 21, and 24 months after the last REACT injection. GFR will be estimated using the Chronic Kidney Disease Epidemiology Collaboration (CKD-EPI) equation that incorporates both serum creatinine and Cystatin C.

Estimated GFR measured at each time point will be summarized by presenting descriptive statistics of raw data and change from baseline values for each treatment group.

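### Does the unnamed covariance matrix and its fallback order in the eGFR slope model (SAP 6.3.4) need to be changed?

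*SAP*

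**What the plan says.** SAP 6.3.4 fits separate linear mixed models to the pre-injection, post-second-injection and whole post-injection periods, with "time (in years, derived as study day/365) as the independent variable". For between-subject variability, "random slopes and intercepts will be included. An unstructured covariance matrix will be used for the model". If that structure fails, "the following structure will be tried in the order listed below (decreasing number of parameters) until the one of them fit the model": ARMA(1,1), AR(1), CS and VC, in that order. For the two post-injection models "the same procedure as for the pre-injection period will be followed". On the data used, "The model will include unscheduled visits".

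The results table gives, per period, the "number of subjects included in the model, the estimated slope for the time variable, and the associated standard error". The only failure described is total: "If no model can be fit, the table will simply display a message" saying that the model did not converge. SAP 9 plans no hypothesis test. SAP 4.1 requires double programming until the two outputs agree.

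**The concern.** Two different matrices could be meant: the 2×2 matrix of the random intercept and slope (G), or the visit-by-visit residual matrix (R). The sentence follows directly on the random effects, which points to G. ARMA and AR structures and the remark about decreasing parameter counts sit more naturally with R. Two programmers could therefore write different models, and the SAP has no rule to settle the difference.

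Neither reading makes the list look well chosen. On G, an intercept variance (eGFR units squared) is set equal to a slope variance (eGFR units per year, squared), and the only fallback with free variances comes last. On R, an unstructured matrix on top of two random effects is over-parameterised, CS repeats the random intercept, and AR(1) and ARMA(1,1) treat unequal gaps as equal.

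The SAP also leaves open whether an estimate on the boundary (a zero variance or a correlation of ±1) counts as a failed fit. The pre- and post-injection rows of the slope table could then carry standard errors from different covariance models without the reader knowing.

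**Working it through.** **Inputs.** From the documents: up to 10 subjects (SAP 9); two random effects (SAP 6.3.4); "serial measurements of eGFR obtained at 1, 3, 6, 12, 15, 18, 21, and 24 months after the last REACT injection" (Protocol 9.4), which is 8 times, or 12 if all laboratory visits after the last injection in Protocol Table 2 count; entry eGFR 14 to 20 (Protocol 5.1), so a uniform spread has SD (20 − 14)/√12 = 1.73. Assumed, because the documents give nothing: mean slope −3 per year; slope SD 4, 1.73 or 1 per year with residual SD 1.5, 1.5 or 1.0 respectively. The plan states no variance or standard error, so there is no figure of its own to reproduce.

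**1. Parameter counts.** Unstructured of dimension q has q(q+1)/2 parameters.

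| Structure | G (2×2) | R (8 visits) |
|---|---|---|
| Unstructured | 3 | 36 |
| ARMA(1,1) | 3 nominal, 2 identified | 3 |
| AR(1) | 2 | 2 |
| CS | 2 | 2 |
| VC | 2 | 1 |

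The counts do not fall strictly on either reading. For unstructured R plus the random effects, 36 + 3 = 39 parameters describe 36 distinct variances and covariances (78 + 3 = 81 for 78 at 12 visits), assuming common visit days. CS in R plus the random effects has 2 + 3 = 5 parameters, of which 4 are identified.

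**2. The G reading is one model three times.** For a 2×2 matrix, ARMA(1,1) is σ²[1, γ; γ, 1], and its ρ first enters at lag 2, which does not exist here. AR(1) is σ²[1, ρ; ρ, 1]. CS has one common variance and one covariance. All three say: equal variances, free correlation.

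**3. How often a fallback is reached (G reading).** REML fits, n = 10, 400 runs in each of 9 settings (post-second injection, pre-injection with up to 24 months of history, and pre-injection with 6 months; three slope SDs each):

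- Trigger = non-convergence: 0 of 9 × 400 = 3,600 unstructured fits.
- Trigger = boundary estimate, tied structure then used: post-second 120, 90 and 58 of 400 (30%, 22.5%, 14.5%); 24-month history 11, 15 and 17 (3-4%); 6-month history 11, 100 and 137 (3-34%).

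The post-second rate depends on the set-up. With the scheduled visits, including Month 9 (which Protocol 9.4 omits but Protocol 6.5 and Table 2 include), reruns put 14-21% of post-second fits at the boundary. With the 8 times and a between-subject level change at the second injection (SD 1.5, assumed), 33/33/23% fell to 5/13/6%. For the whole post-injection model it was 2-3%.

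**4. Size when the tied structure is used.** Mean standard errors in three of the settings:

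| Setting | Tied | Unstructured | VC | Actual error |
|---|---|---|---|---|
| Post-second, slope SD 4 | 0.92 | 1.18 | 1.20 | 1.27 |
| Post-second, slope SD 1 | 0.30 | 0.34 | 0.35 | 0.35 |
| 6-month history, slope SD 1 | 0.72 | 0.55 | 0.54 | 0.67 |

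Tied over unstructured: 0.92/1.18 = 0.78; 0.30/0.34 = 0.88; 0.72/0.55 = 1.31. Eight of the nine settings differ by 4-31%, four lower and four higher. The ninth is +93% and rests on 17 runs. The slope is identical in balanced settings and moves by at most 0.22 per year otherwise. A second, smaller simulation, which compared the tied and unstructured fits over all its runs, gave ratios of 0.74 to 1.39.

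**5. R reading.** Unstructured R cannot realistically be estimated from 10 subjects, so a fallback would be normal here. AR(1) by visit order differed from a spatial-power model on actual time by 1.7-5.0% in standard error. The second simulation put AR(1) and ARMA(1,1) within about 8% of the unstructured-G fit, and CS gave the same standard error as VC.

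**6. Would unstructured-then-VC be better?** Over all runs, standard error divided by empirical SD was 0.97-1.11 for the SAP's sequence and 0.96-1.07 for unstructured then VC. In the runs that fell back, the tied value was nearer the actual error in 5 settings, VC in 3, and 1 was level. In the third row above, VC misses by 0.67 − 0.54 = 0.13 and the tied structure by 0.72 − 0.67 = 0.05. In the first row VC misses by 0.07 and the tied structure by 0.35.

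**The case for a change.** The best case for acting is that the amendment would cost only wording and a table column. Protocol section 2 proposes that treatment slows eGFR decline, and each subject is his or her own control, so readers will set the pre- and post-injection rows side by side. Their standard errors should not come from different, unlabelled models. The tied structure is arbitrary in scale: in the 6-month setting with slope SD 1, refitting in months turns 0.71 into 2.06. VC does not depend on the time unit and stayed within 6% of the unstructured fit in all nine settings.

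Part of this stands. The matrix is not named, the trigger is not defined, and the table does not show the structure used. The rest is weaker. SAP 6.3.4 fixes time in years, so the months result cannot occur under this plan. Closeness to the unstructured fit is little recommendation in runs where that fit is the one judged unusable. VC also drops the intercept-slope correlation and can understate the error: 0.23 against 0.37 with up to 24 months of history and slope SD 1.

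**Conclusion.** No change to the plan follows. This is a gap in detail that analysts can fill sensibly. Placement after the random effects makes G the natural reading, non-convergence is the only failure the SAP describes, and the structure used can be footnoted. Double programming would bring any difference of reading into the open.

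On the G reading with non-convergence as the trigger, the simulated effect is nil. With a boundary trigger, the standard error moves by roughly 10-30% in most settings, in either direction, while the slope is almost unchanged. On the R reading the shift is a few percent. The quantity affected is the standard error of an exploratory slope in at most 10 subjects. No test, confidence interval or between-period contrast uses it, and per-subject plots are planned beside it. The substantive alternative, moving directly to VC, is a reasonable simplification but gives no demonstrated gain in accuracy.

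This rests on assumed slope and residual SDs and on purpose-written REML code rather than SAS, so the convergence rate in the actual analysis could differ. The nine-setting simulation did not cover the whole post-injection model; for that period only the boundary rate was checked in a rerun, and the smaller simulation gave standard-error ratios.
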